5.7 Adherence/Compliance

Compliance will be measured by pill counts and patient diaries. For telehealth visits, we will ask participants to photograph unused pills for remote pill counts and patient pill diaries and compliance will be assessed remotely. Compliance is defined as 85% of the total dose over the entire study period. A participant diary will be used to monitor daily compliance (Appendix C). Participants will be instructed to record the time the study drug was taken each day in the diary, as well as any potential side effects. Diaries will be reviewed and compliance will be assessed at Study Visits 2-4.

Phone calls will be made to study participants every four weeks (\pm 7 days) to monitor compliance. Participants will be asked if they missed any doses of medication, and the dates of all missed doses will be recorded. The study agent diary will be reviewed with participants at every visit. Participants who report having taken < 85% of the study drug doses between phone calls, or whose pill count at a study visit reveals < 85% compliance, will be called every two weeks (\pm 3 days) to monitor compliance.

The participant will be asked at registration if they would like to receive reminder emails or text messages regarding the study medication. Messages will be sent daily for the first week; in following weeks, messaging will be targeted to participants having difficulty remembering their dose. In addition, phone calls will be made to all study participants during the week before their final visit (Visit 4) to remind them to take the study drug every day until the last study visit. Participants will also be reminded to bring any leftover study drugs and the study diary with them to each visit.

Capsule counts will be performed at Study Visits 2, 3, and 4 to assess compliance. If less than 85% of the dose has been consumed during the study period, the subject will be considered non-compliant. All participants that receive a study agent for any period of time will be evaluable for toxicity.

6. PHARMACEUTICAL INFORMATION

6.1 Study Agent (IND# (Exempt), IND Sponsor: NCI/Division of Cancer Prevention)

Simvastatin (Zocor) 40 mg and simvastatin placebo will be supplied by NCI, DCP. Simvastatin is a lipidlowering agent that is derived synthetically from a fermentation product of *Aspergillus terreus*. After oral ingestion, simvastatin, which is an inactive lactone, is hydrolyzed to the corresponding β -hydroxyacid form. This is an inhibitor of 3-hydroxy-3-methylglutaryl-coenzyme A (HMG-CoA) reductase, and catalyzes the conversion of HMG-CoA to mevalonate, which is an early and rate-limiting step in the biosynthesis of cholesterol.

The empirical formula of simvastatin is $C_{25}H_{38}O_5$ and its molecular weight is 418.57. It is a white to offwhite, nonhygroscopic, crystalline powder that is practically insoluble in water, and freely soluble in chloroform, methanol, and ethanol. Simvastatin tablets for oral administration contain 40 mg of simvastatin and the following inactive ingredients: ascorbic acid, citric acid, hydroxypropyl cellulose, hypromellose, iron oxides, lactose, magnesium stearate, microcrystalline cellulose, starch, talc, and titanium dioxide. Butylated hydroxyanisole is added as a preservative.

Information on the placebo will be provided when available.

6.2 Reported Adverse Events and Potential Risks

The most common reported adverse events (incidence $\geq 5.0\%$) are upper respiratory infection, headache, abdominal pain, constipation, and nausea. Other adverse events reported in clinical trials (<5%) were diarrhea, rash, dyspepsia, flatulence, and asthenia.

Persistent increases in serum transaminases (to more than $3 \times$ the ULN) have occurred in approximately 1% of patients who received simvastatin in clinical studies. When drug treatment was interrupted or discontinued in these patients, the transaminase levels usually fell slowly to pretreatment levels. The increases were not associated with jaundice or other clinical signs or symptoms. It is recommended that liver function tests be performed before the initiation of treatment, and thereafter when clinically indicated.

Simvastatin occasionally causes myopathy manifested as muscle pain, tenderness, or weakness with creatine kinase above ten times the ULN. Myopathy sometimes takes the form of rhabdomyolysis with or without acute renal failure secondary to myoglobinuria, and rare fatalities have occurred. The risk of myopathy is increased by high levels of statin activity in plasma. Predisposing factors for myopathy include advanced age (≥65 years), female gender, uncontrolled hypothyroidism, and renal impairment. The risk of myopathy, including rhabdomyolysis, is dose related. The risk of myopathy and rhabdomyolysis is increased by high levels of statin activity in plasma. Simvastatin is metabolized by the cytochrome P450 isoform 3A4 (CYP3A4). Certain drugs which inhibit this metabolic pathway can raise the plasma levels of simvastatin and may increase the risk of myopathy. These include itraconazole, ketoconazole, posaconazole, voriconazole, the macrolide antibiotics erythromycin and clarithromycin, the ketolide antibiotic telithromycin, HIV protease inhibitors, boceprevir, telaprevir, the antidepressant nefazodone, cobicistat-containing products, or grapefruit-containing products. Combination of these drugs with simvastatin is contraindicated. If short-term treatment with strong CYP3A4 inhibitors is unavoidable, therapy with simvastatin must be suspended during the course of treatment.

Increases in HbA1c and fasting serum glucose levels have been reported with HMG-CoA reductase inhibitors, including simvastatin.

6.3 Availability

Simvastatin and matching placebo are investigational agents supplied to investigators by DCP, NCI. Simvastatin 40 mg and matching placebo will be supplied as over-encapsulated tablets for oral administration. Simvastatin and matching placebo will be packaged with 120-count 40 mg capsules per bottle. Each participant will be given/shipped one bottle at Study Visit 1 and one bottle at Study Visit 3 (Month 3). Please see the NWU2015-06-03 pharmacy manual for shipping procedures.

6.4 Agent Distribution

Agents will only be released by NCI, DCP after documentation of NCI Central IRB (CIRB) approval of the DCP-approved protocol and consent is provided to DCP and the collection of all Essential Documents is complete (see DCP website for description of Essential Documents).

NCI, DCP-supplied agents may be requested by the Investigator (or their authorized designees) at each

Organization. DCP guidelines require that the agent be shipped directly to the institution or site where the agent will be prepared and administered. DCP does not permit the transfer of agents between institutions (unless prior approval from DCP is obtained). DCP does not automatically ship agents; the site must make a request. Agents are requested by completing the DCP Clinical Drug Request form (NIH-986) (to include complete shipping contact information) and faxing or mailing the form to the DCP agent repository contractor:

[name] MRIGlobal DCP Repository [name] [contact] [contact] Emergency [contact]

6.5 Agent Accountability

The Investigator, or a responsible party designated by the Investigator, must maintain a careful record of the inventory and disposition of all agents received from DCP using the NCI Drug Accountability Record Form (DARF). The Investigator is required to maintain adequate records of receipt, dispensing, and final disposition of study agent. This responsibility has been delegated to the study pharmacists: [name]., Investigational Drug Pharmacist at Cedars-Sinai Medical Center; [name], Pharm. D., Investigational Drug Pharmacist at Northwestern Memorial Hospital; [name]. at Georgetown University, and [name]. at the University of Puerto Rico. Include on receipt record from whom the agent was received and to whom study agent was shipped, date, quantity and batch or lot number. On dispensing record, note quantities and dates study agent was dispensed to and returned by each participant.

6.6 Packaging and Labeling

Simvastatin and placebo will be packaged by NCI, DCP.

Each bottle will be labeled with a one-part label identifying study specific information, such as study title, DCP protocol number, dosing instructions, recommended storage conditions, the name and address of the distributor, randomization number, and a caution statement indicating that the agent is limited by United States law to investigational use only and the agent should be kept out of reach of children.

6.7 Storage

The DCP Drug Repository, MRIGlobal, will distribute the study agent directly to each participating site. Study agents will be stored in a safe, secure, temperature monitored limited access drug storage area specifically for research medication at the Research Pharmacy at each site. Study agents shall be maintained at a controlled room temperature [between 15-30°C] by the Research Pharmacy at each site and once dispensed, the subjects will be instructed to store the drug in their homes protected from light, heat, and moisture. MRIGlobal will be notified in the event of a temperature excursion below 15°C or above 30°C for 24 hours continuously. MRIGlobal will evaluate the temperature excursions on a case-by-case basis.

6.8 Registration/Randomization

- 1. A study coordinator must upload into the Northwestern Clinical Trials Management System, a signed and complete informed consent along with HIPAA authorization and a completed eligibility form for each participant identified as eligible to be entered into the study.
- 2. All participants must be registered in the Northwestern University Robert H. Lurie Comprehensive Cancer Center Clinical Trials Management System (CTMS). Participants must not start protocol treatment prior to registration in the Lurie Cancer Center CTMS.
- 3. After registration in the CTMS, participants will be assigned a participant identification number and a randomization number when applicable.
- 4. An NCPC Quality Assurance Monitor will submit the following into the REDCap Randomization Information Form: (1) Study Number, (2) Site, (3) Pharmacist Email(s), (4) Participant ID, (5) Participant Initials, and (6) Randomization Date.
- An Automatic Treatment Assignment Notification email will be sent to the research pharmacist(s) containing: (1) Study Number, (2) Site, (3) Participant ID, (4) Participant Initials, (5) Randomization Date, and (6) Treatment Assignment.
- 6. The clinical research coordinator(s) will receive a Confirmation of Registration containing the PID via email.
- 7. The following people will have a copy of the un-blinded randomization log: the study statistician at NU, the Quality Assurance Team at NU, and the Investigational Pharmacists at each site. The following people will have access to the REDCap study project containing randomization information: the study statistician at NU and the Quality Assurance Team at NU. The study statistician will set up randomization blocks.

When possible, the study coordinator will notify an NCPC Quality Assurance Monitor and/or send an email to [contact] prior to registering a participant. Prior notification is required for participant randomizations outside the normal business hours of Monday-Friday 9:00am-5:00pm CT.

6.9 Blinding and Unblinding Methods

The research pharmacist will manage the investigational agent. The blind will be maintained through the effort of the research pharmacist, and the pharmacy. Unblinding will only occur when it is deemed medically necessary, and will only take place after consultation with the NCI, DCP Task Order Monitor. If the NCI Task Order Monitor cannot be reached and the participant requires emergency care, the Study Chairman may authorize the site PI to break the blind. The date and reason for breaking the blind must be submitted by the site PI to the Study Chairman and the NCI Task Order Monitor as soon as possible.

The NCI Medical Monitor must be notified that the blind has been broken. The NCI CIRB and the IRB at the site where the blind is broken will also be notified.

DCP Medical/Task Order Monitor [name] [name], FACS NCI/Division of Cancer Prevention [name] [name] 5[name] 20892 [contact] [contact] Email: [contact]

6.10 Agent Destruction/Disposal

At the completion of investigation, all unused study agent will be destroyed according to local institutional procedures. Destruction records must be provided to MRIGlobal at the end of the study.

7. CLINICAL EVALUATIONS AND PROCEDURES

7.1 Schedule of Events

Procedure	Pre- Screen ¹	Screen 1 ² ^	Study Visit 1 ³	Study Visit 2 ⁴	Study Visit 3 ⁵	Study Visit 4 ^{6^}	Follow- Up
Assess eligibility (review inclusion/exclusion criteria) and recruitment	X	X					
Informed Consent and HIPAA authorization		Х					
Abdominal imaging (CT, MRI, ultrasound) ⁷	X					Х	
Review study requirements	X	Х	Х	Х	Х		
Review medical history, medications, and laboratory test results	X	X	Х	Х	Х	X	
Blood hematology: Complete Blood Count and Automated Differential (CBDF)		Х	Х	Х	Х	Х	
Blood chemistry: Comprehensive Metabolic Panel (CMPL)		Х	Х	Х	Х	Х	
Blood test: Prothrombin Time (PT/INR)		Х				Х	
Urine pregnancy test ⁸		Х					
Registration and randomization to simvastatin or placebo		-	X				
Demographics (race, ethnicity, education)			Х				
Assess symptoms and ECOG performance status		X	Х	Х	Х	X	
Physical assessment, assess liver disease sequelae		Х				Х	
Vital signs assessment, measure weight		Х	Х	Х	Х	Х	
Blood test: Lipid Panel			Х		Х	Х	
Blood test: Hemoglobin A1C (HbA1C)			Х		Х	Х	
Blood test: Creatine Phosphokinase (CPK)			Х				
Collect blood specimen for research9			Х			Х	
Conduct liver elastography (FibroScan)			Х			Х	
Interviewer-administered risk questionnaire			Х				
Self-administered VioScreen [®] food frequency questionnaire ¹¹			Х				
Dispense study agent and diary			Х	Х	Х		
Collect study agent and diary				Х	Х	Х	
Review study diary				Х	Х	Х	
Assess compliance (pill count)				Х	Х	Х	
Assess adverse events				Х	Х	Х	Х
Telephone contact ¹⁰	X	Х	Х	Х	Х	Х	Х

Procedure	Pre-	Screen	Study	Study	Study	Study	Follow-
riocedure	Screen ¹	1 ^{2^}	Visit 1 ³	Visit 2 ⁴	Visit 3 ⁵	Visit 4 ^{6^}	Up

¹Medical chart review for patients who are liver transplant candidates and have an upcoming appointment with a study hepatologist to determine initial eligibility; recruitment of potentially eligible patients

² Obtain consent of potentially eligible patients; thorough review of patient's medical history, concomitant medications, and laboratory test results; evaluation of inclusion and exclusion criteria; and assessments for final determination of eligibility. Screen 1 eligible/consented patients will be registered and randomized to the intervention (simvastatin or placebo).

³ Study Visit 1 (baseline measurements/initiation of the intervention) will occur 0-30 days after Screen 1.

⁴ Study Visit 2 will occur 1 month (\pm 14 days after initiation of the intervention.

⁵ Study Visit 3 will occur 3 months (\pm 14 days) after initiation of the intervention.

⁶ Study Visit 4 (last day of study intervention) will occur 6 months (\pm 30 days) after initiation of the intervention.

⁷ Abdominal imaging results will be reviewed during pre-screen medical chart review to determine initial eligibility. An abdominal image (CT, MRI, or ultrasound), which is a standard of care procedure for the study population, will be taken at Study Visit 4. The abdominal imaging may be done up to the end of follow-up for the study (3 months after completion of Study Visit 4 [Visit 4 ± 3 months]).

⁸ Because statins are known to be teratogenic, women able to become pregnant will be required to have a urine pregnancy test. Women \geq 50 years of age who have not had a menstrual period in the past year; and women who have had a hysterectomy, both ovaries removed, or a tubal ligation; will not be required to have a pregnancy test. Women who are pregnant will be excluded from the study.

⁹ Blood collection for research: A 20 mL blood specimen will be collected from each participant at Study Visits 1 and 4 for research purposes. Ten mL of blood will be drawn for measurement of protocol-specific biomarkers (AFP, AFP-L3%, IL-6, and bile acids) and 10 mL of blood will be drawn for DNA extraction and use in future studies.

¹⁰ Telephone contact with patients during the screening period to assess eligibility, introduce the study, and answer questions. Telephone contact every four weeks (\pm 7 days) during the intervention to assess compliance and adverse events. Follow-up telephone contact on days 30 \pm 7, 60 \pm 7, and 90 \pm 7 after completion of Study Visit 4 to assess adverse events. ¹¹ Please see Appendix J for VioScreen[®] instructions for participants.

7.2 **Pre-Study Evaluation and Baseline Testing**

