4.1.2 Age ≥ 18 years

- 4.1.3 ECOG performance status ≤ 1 (Karnofsky $\geq 70\%$; see Appendix A)
- 4.1.4 Participants must have acceptable organ, hepatic and renal function as defined below:

Leukocytes	$\geq 2,500/\text{microliter}$
Absolute neutrophil count	\geq 1,500/microliter
Platelets	\geq 50,000/microliter
Hemoglobin	$\geq 8 \text{ g/dL}$
Total bilirubin	$\leq 3 \times$ institutional upper limit of normal (ULN)
AST (SGOT)/ALT (SGPT)	\leq 5 × institutional ULN
Creatinine	$\leq 1.5 \times \text{institutional ULN}$
010000000	

Patients whose lab results meet the inclusion criteria after the Screen 1 blood tests will be included in the trial.

4.1.5 Women who are able to become pregnant must have a confirmed negative pregnancy test result prior to enrollment. Women \geq 50 years of age who have not had a menstrual period in the past year; and women who have had a hysterectomy, both ovaries removed, or a tubal ligation; will not be required to have a pregnancy test.

4.1.6 The effects of simvastatin on the developing human fetus at the recommended therapeutic dose are unknown. For this reason, women who are able to become pregnant must agree to use adequate contraception (hormonal or barrier method of birth control; abstinence) prior to study entry and for the duration of study participation. Should a woman become pregnant or suspect she is pregnant while participating in this study, she should inform her study physician immediately.

4.1.7 Ability to understand and the willingness to sign a written informed consent document and medical release

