5.2 Study Agent Administration

Patients will self-administer the 40 mg capsule of simvastatin or placebo daily in the evening. Patients will be instructed to take the study agent at bedtime or with an evening meal. Each participant will be given/shipped one bottle of 120 capsules at Study Visit 1 (90-day supply + buffer) and one bottle of 120 capsules (90-day supply + buffer) at Study Visit 3 (Month 3).

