- 5. A blood specimen (approximately 15 mL) will be collected from patients for blood tests to confirm eligibility. If a patient's lab results are current (within the past 30 days) in the medical record and within eligibility range, their blood will not be drawn at the Screen 1 visit. Otherwise, the patient's blood will be drawn to confirm eligibility. A Complete Blood Count and Automated Differential (CBDF) (for leukocytes, neutrophils, platelets, and hemoglobin), a Comprehensive Metabolic Panel (CMPL) (for liver enzymes (AST/ALT) and for total bilirubin, creatinine, and sodium (required for calculation of the MELD score)), and Prothrombin Time (PT/INR) (required for calculation of MELD) will be done to confirm that blood levels are within the eligibility requirements (acceptable organ function, AST/ALT ≤5x upper limits of normal, and MELD ≤ 20). See Appendix E for Clinical Laboratory Minimum Test Requirements.
- 6. Women who are able to become pregnant will be required to have a pregnancy test because statins are known to be teratogenic. Women ≥ 50 years of age who have not had a menstrual

period in the past year; and women who have had a hysterectomy, both ovaries removed, or a tubal ligation; will not be required to have a pregnancy test.

Patients with a MELD score >20, AST/ALT >5x ULN, or other lab results that do not meet the eligibility criteria; and women who are pregnant will be excluded from the study. Following eligibility screening, and prior to Study Visit 1, consented patients who qualify for the study after the eligibility evaluations will be registered and enrolled in the study and randomized to the intervention (simvastatin or placebo). The Screen 1 MELD calculation will be used as the baseline MELD score, and Screen 1 lab values for AST, ALT, and platelets (PLT) will be used to calculate the baseline FIB-4 score.

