7.2.3 Study Visit 1 – Baseline Testing and Initiation of the intervention

Study Visit 1 (Baseline measurements) will occur 0-30 days after the Screen 1 eligibility visit. The following procedures will be performed during this visit:

- 1) Review of medical history, medications, and laboratory test results
- 2) Symptom assessment and ECOG performance status
- 3) Vital signs assessment, including blood pressure, heart rate, and temperature; and measurement of height and weight
- 4) Blood collection for clinical labs (approximately 10 mL). Laboratory blood tests will be done for a Lipid Panel, hemoglobin A1C, and Creatine Phosphokinase (CPK) to establish baseline levels prior to initiating the study agent. CBDF and CMPL lab results from the Screen 1 eligibility visit will be used to establish patient-specific references prior to initiation of therapy. If blood tests were not done at the Screen 1 visit for a CBDF and CMPL; and lab results within 30 days prior to this visit for these tests are not available in the medical record, a CBDF and CMPL will be done at this visit. See Appendix E for Clinical Laboratory Minimum Test Requirements.
- 5) Blood collection for research (20 mL). Ten mL of blood will be collected for measurement of protocol-specific biomarkers (AFP, AFP-L3%, IL-6, and bile acids) and 10 mL of blood will be drawn for DNA extraction and use in future studies.
- 6) Liver elastography (FibroScan). A FibroScan examination will be conducted. Participants will be instructed to refrain from eating for 3 hours before the FibroScan examination. The FibroScan will be used as a non-invasive measurement of liver stiffness.
- Interviewer-administered baseline questionnaire to obtain demographic information (detailed race and ethnicity, education); medical and medications history; alcoholic beverage consumption; tobacco smoking; and anthropometry (Appendix F)
- 8) Food frequency questionnaire (FFQ). The VioScreen[®] graphical dietary assessment will be selfadministered to capture usual diet over the last 30 days.
- 9) Review of study requirements
- 10) Dispense the study agent (one bottle of 120 capsules) and review instructions for how to take it
- 11) Dispense and review the study diary

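### The only scheduled pregnancy test is at Screen 1, up to 30 days before first dispensing; repeating it at Study Visit 1 is a small, cheap safety improvement

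*Combined protocol and SAP*

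**What the plan says.** The reason for testing is in Section 7.1, footnote 8: "Because statins are known to be teratogenic, women able to become pregnant will be required to have a urine pregnancy test". The schedule table has one mark in the urine pregnancy test row, under Screen 1, and Section 7.2.2 (item 6) lists the test among the Screen 1 procedures.

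Footnote 3 of the same schedule sets the interval to treatment: "Study Visit 1 (baseline measurements/initiation of the intervention) will occur 0-30 days after Screen 1". Section 7.2.3 lists 11 procedures for Study Visit 1. Item 10 is "Dispense the study agent (one bottle of 120 capsules) and review instructions for how to take it", and none of the 11 is a pregnancy test.

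On eligibility, criterion 4.1.5 says that women able to become pregnant "must have a confirmed negative pregnancy test result prior to enrollment". Section 7.2.2 places enrolment ahead of the dispensing visit: "prior to Study Visit 1, consented patients who qualify for the study after the eligibility evaluations will be registered and enrolled in the study".

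Criterion 4.1.6 adds two safeguards. These women "must agree to use adequate contraception (hormonal or barrier method of birth control; abstinence) prior to study entry and for the duration" of study participation, and "Should a woman become pregnant or suspect she is pregnant while participating in this study, she should inform her study physician immediately".

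**The concern.** The test exists to keep a pregnant woman from starting simvastatin, but the protocol verifies pregnancy status at enrolment and not when exposure begins. A pregnancy conceived after Screen 1, or too early to detect at that visit, would not be picked up before the first capsule. No test is scheduled at any later visit, so a pregnancy missed at this point comes to light only if the participant recognises and reports it.

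What is at stake is fetal exposure to a drug that the protocol treats as reason enough to exclude pregnant women. The point has no bearing on the primary endpoint, power or type I error.

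**Working it through.** **Where the test falls relative to the first dose**

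| Step | Place in protocol | Timing | Pregnancy test? |
|---|---|---|---|
| Screen 1 | 7.1 schedule; 7.2.2 item 6 | Day 0 | Yes |
| Enrolment and randomisation | 7.2.2 (before Visit 1); 7.1 table (Visit 1 column) | Up to Visit 1 | Screen 1 result suffices |
| Study Visit 1, first bottle dispensed | 7.1 footnote 3; 7.2.3 item 10 | 0-30 days after Screen 1 | None |
| Study Visits 2, 3 and 4 | 7.3.1, 7.3.2, 7.4.1 | Months 1, 3 and 6 | None |
| Telephone calls | 7.3.3 | Every four weeks | Pregnancy not on the checklist |

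Section 7.2.2 and the schedule table differ on whether randomisation comes before Visit 1 or at it. This does not affect the point. Criterion 4.1.5 sets no maximum interval between test and first dose, so under either reading the Screen 1 result meets it and nothing triggers a repeat.

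Section 5.2 says "Each participant will be given/shipped one bottle of 120 capsules at Study Visit 1". If the bottle is shipped, the first capsule may be taken somewhat after Visit 1, so the interval from test to first dose could slightly exceed 30 days.

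**Expected size**

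Inputs from the documents:
- Women expected (Table 1, Section 4.4): 20 + 9 = 29 of 80.
- Allocation 1:1 (Section 13.2).

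Assumptions, not in the documents:
- Share of these women able to become pregnant: 10-30%.
- Monthly pregnancy risk under the required contraception: 0.5-3%.
- Every woman has the full 30-day gap. This is the maximum, so it overstates the time at risk.

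Women to be tested:
- Low: 29 × 0.10 = 2.9
- High: 29 × 0.30 = 8.7
- On simvastatin: 2.9 / 2 = 1.45 to 8.7 / 2 = 4.35

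Expected pregnancies in the gap = women × monthly risk:

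| | Low | High |
|---|---|---|
| Both arms | 2.9 × 0.005 = 0.0145 | 8.7 × 0.03 = 0.261 |
| Simvastatin arm | 1.45 × 0.005 = 0.007 | 4.35 × 0.03 = 0.131 |

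The most likely number of pregnancies in this window is therefore zero.

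**Effect of a repeat test.** The longest interval from test to dispensing falls from 30 days to 0, because both happen at the same visit. Sample size, power and alpha do not change.

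**The case against.** The strongest reply is that no rule is broken. A negative result is required before enrolment, contraception is mandatory throughout, and a suspected pregnancy must be reported at once. Visit 1 also includes a history and medication review, a symptom assessment and a review of study requirements, all listed before dispensing, and any of these gives an opening to raise a suspected pregnancy. This stands to the extent that the plan is not contradictory and the risk is already low. But none of these steps is stated to ask about pregnancy, and none can detect one that the woman does not suspect.

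The hazard is also worded more softly elsewhere. Criterion 4.1.6 calls the fetal effects at the recommended dose unknown, and 4.2.5 speaks only of potential effects. That is fair, but under every wording pregnant women are excluded, so the purpose of the test is the same.

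A sharper objection is that six months of dosing carry about six times the risk of the pre-dose gap: on the same assumptions, 0.0145 × 6 = 0.09 to 0.261 × 6 = 1.6 pregnancies in both arms. The on-treatment period is left to contraception and self-report, so why should those not suffice for one month more? This is correct as arithmetic, and the repeat test does nothing for the later period. The difference is that at Visit 1 exposure can still be prevented altogether, at a visit that takes place anyway.

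Finally, the consent form was not available for this review, so a repeat test mentioned only there cannot be ruled out. The schedule and visit lists that sites work from contain none.

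**Conclusion.** The concern holds as a minor design improvement, not as an error or inconsistency. Pregnancy status is checked 0 to 30 days before first dispensing and not again. The expected effect is very small: about 0.01-0.26 pregnancies in both arms and about 0.01-0.13 on simvastatin. Those ranges depend on the assumed share of women able to become pregnant, the assumed monthly risk, and a full 30-day gap for everyone. Only the 29 women and the 1:1 allocation come from the protocol. The case for change is that the harm could be serious and the remedy costs almost nothing. A urine test at Visit 1 can still miss a very recent conception, so it narrows the gap without fully closing it.

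**What to change.** For the same women, with the exemptions already in footnote 8:

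1. In the Section 7.1 schedule, mark the urine pregnancy test row at Study Visit 1 as well as Screen 1.
2. In Section 7.2.3, add the test ahead of item 10, with the result read before the first bottle is handed over or shipped. It can be waived when Screen 1 and Visit 1 fall on the same day. If the result is positive, do not dispense.
3. In criterion 4.1.5, require a negative result before enrolment and again before first dispensing.

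The cost is one dipstick per woman concerned, about 3-9 in total under the 10-30% assumption, at a visit that already includes a blood draw and FibroScan, plus three short wording changes. The one drawback is that a participant might, rarely, be withdrawn after randomisation but before her first dose.
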